#### **9.6.4 COVID-19 Analyses**

**All analyses will be restricted to participants who remained in REPRIEVE study follow-up as of January 1, 2020. Person years of follow-up will be measured from January 1, 2020.**

**The incidence of COVID-19 diagnoses and COVID-19 hospitalizations will be estimated, including the statin effect on the incidence of COVID-19 and serious COVID-19 disease via estimation of the incidence rate ratio by randomized treatment group. Log binomial regression will be utilized to assess host factors associated with COVID-19 infection as defined by a) SARS-CoV-2 antibody positivity and b) severe disease requiring hospitalization.**

**Analyses will be stratified by global burden of disease region and randomized treatment and control for comorbid conditions (including hypertension, diabetes, kidney disease, and obesity). Further extension of these analyses will evaluate the influence of targeted concomitant medications (such as lopinavir/ritonavir and of ACE inhibitors and ARBs), and COVID-19 vaccination on rates of SARS-CoV-2 infection.**

**In all analyses, death (not due to COVID-19) will be considered a censoring event. Discontinuation of randomized treatment will be ignored in primary analyses; a supportive analysis will censor at randomized treatment discontinuation and use inverse probability of censoring weights (IPCW) to estimate the statin effect when statins are being taken per protocol. Likewise, COVID-19 vaccination will be ignored in the primary analysis; a supportive analysis will censor at COVID-19 vaccination and use IPCW to estimate the statin effect in the absence of COVID-19 vaccination.**

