### 9.2.2.5 Calculated fasting LDL and non-HDL cholesterol level at study entry and annually thereafter as well as change from baseline expressed as absolute change and as a percentage of baseline. For participants with triglycerides >400 mg/dL and <500 mg/dL, direct LDL will be determined and use in the statistical analysis.

9.2.2.6 Time to any of the following adverse events (including recurrent events as appropriate)

- Serious adverse event as defined by ICH criteria
- Incident Diabetes mellitus (DM)
- Grade 3 or 4 ALT
- Grade 3 or 4 myopathy
- **COVID-19 diagnosis**
- **Serious COVID-19 diagnosis (ie, a COVID-19 diagnosis that is Grade 4 or results in hospitalization or death)**

All events will be included regardless of relationship to treatment as determined by sites.

Grading will be defined per the DAIDS Table for Grading the Severity of Adult and Pediatric Adverse Events, corrected Version 2.1, July 2017.

See [section 11.4](#) for link to the document.

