**For COVID-19 outcomes, time will be measured from January 1, 2020.**

**9.2.2.7 Antibody-positive COVID-19 infection assessed cross-sectionally at specific calendar time points from samples collected annually.**

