#### 9.4.4 Power Considerations for COVID-19 Objectives

In March 2020, when SARS-CoV-2 infections and COVID-19 diagnoses were emerging in REPRIEVE enrollment areas, approximately 6650 REPRIEVE participants remained in follow-up.

It was hypothesized that 30% of REPRIEVE participants will be antibody positive for exposure to SARS-CoV-2. This rate is considered a conservative estimate based on widespread successful implementation of mitigation strategies. Recent studies from NYC and other large US urban areas indicate infection rates of up to 30%, and this is anticipated to increase further, especially in less-developed Global Burden of Disease regions that recruited into REPRIEVE. With the use of comprehensive sensitive and specific state of the art antibody testing, as proposed in this supplement, we will be well-poised to capture a significant number of cases, independent of any differences in more localized testing rates.

Allowing for 5% additional losses to follow-up, this will yield approximately 2000 cases and 4650 controls for analyses, including about 200 hospitalizations (10% of infections, ie, serious disease), and will provide ample numbers for the proposed epidemiology, pathobiology, genetic, and clinical investigations (see [Table 9.4.4-1](#)). For example, with this rate of antibody positivity, we will be able to estimate infection risk with a precision of at least  $\pm 1.2\%$ , and will have 90% power to show a 12% reduction in the infection risk in the pitavastatin group ( $RR=0.88$ , 30% risk in the placebo group compared to 26% risk in the pitavastatin group), and 80% power to detect a 35% relative risk reduction ( $RR=0.65$ ) in serious disease (see table cells in blue font). Detectable effect sizes for antibody positivity rates of 15%-30% and power of 80%-90% are shown in the table below.

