**Table 9.4.4-1: Detectable Effect Sizes for Antibody Positivity Rates of 15%-30% and Power of 80%-90%**

Power		Proportion of Participants COVID-19 Antibody Positive (Control)			
		30%	20%	15%	
Precision to estimate infection risk	-	$\pm 0.012\%$	$\pm 0.0135\%$	$\pm 0.015\%$	
Detectable risk reduction with given power	90%	12% ( $RR=0.88$ )	15% ( $RR=0.85$ )	18% ( $RR=0.82$ )	
	85%	11% ( $RR=0.89$ )	14% ( $RR=0.86$ )	17% ( $RR=0.83$ )	
	80%	10% ( $RR=0.90$ )	13% ( $RR=0.87$ )	16% ( $RR=0.84$ )	
		Proportion of COVID-19 antibody positives experiencing serious disease			
		10%	20%	10%	20%

Detectable risk reduction with given power	90%	40% (0.60)	29% (0.71)	48% (0.52)	35% (0.65)	55% (0.45)	40% (0.60)
	85%	38% (0.62)	27% (0.73)	45% (0.55)	33% (0.67)	51% (0.49)	38% (0.62)
	80%	35% (0.65)	25% (0.75)	43% (0.57)	31% (0.69)	48% (0.52)	35% (0.65)

*\* Assumes sample size of 6650 with evaluable COVID-19 antibody results equally distributed between pitavastatin and placebo groups (see text for rationale for this number).*

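### The severe-disease outcome in the COVID-19 host-factor model (Protocol 9.6.4, outcome b) is narrower than the serious COVID-19 endpoint in 9.2.2.6, so a COVID-19 death or Grade 4 case outside hospital is, read literally, a non-case.

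*Protocol*

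**What the plan says.** Protocol 9.2.2.6 lists among its time-to-event outcomes a "Serious COVID-19 diagnosis (ie, a COVID-19 diagnosis that is Grade 4 or results in hospitalization or death"). Three routes lead to an event: grade, admission or death.

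Protocol 9.6.4 then uses two outcome descriptions. The randomized comparison estimates the "statin effect on the incidence of COVID-19 and serious COVID-19 disease via estimation of the incidence rate ratio", a term that can follow 9.2.2.6. The host-factor models take outcomes "as defined by a) SARS-CoV-2 antibody positivity and b) severe disease requiring hospitalization", so death and Grade 4 are not named. On deaths, the same section says: "In all analyses, death (not due to COVID-19) will be considered a censoring event". It does not say how a COVID-19 death is coded in the log-binomial models.

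The power text in 9.4.4 also equates serious disease with admission, "including about 200 hospitalizations (10% of infections, ie, serious disease"). For outcome (a), 9.2.2.7 describes "Antibody-positive COVID-19 infection assessed cross-sectionally at specific calendar time points from samples collected annually".

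Section 9.6.4 refers further detail to the main REPRIEVE SAP. That document was not supplied; the SAP at hand covers only the mechanistic substudy A5333s.

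**The concern.** Two definitions of the severe end of the same disease stand a few pages apart, and nothing explains the difference. Under (b) as written, someone who dies of COVID-19 without being admitted does not meet the outcome. That death is not due to another cause, so the censoring rule does not remove the person either. The worst outcome is then grouped with never having had severe disease. Grade 4 disease managed outside hospital is treated the same way.

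Two things are at stake. Some serious cases are lost from an analysis that expects only about 200. And if the chance of being admitted, given serious disease, varies with the host factor under study, the estimated RR mixes severity with admission. The host-factor result and the randomized result would also describe different outcomes under similar names.

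**Working it through.** **The plan's own figures.** Inputs from Protocol 9.4.4 and Table 9.4.4-1: 6650 evaluable participants split equally (3325 per arm), 30% antibody positive, 10% of those with serious disease. From 9.6.1: two-sided 5% tests.

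- Infections: 6650 × 0.30 = 1995. Hospitalizations: 1995 × 0.10 = 199.5, matching the stated 2000 and 200.
- Power for RR 0.65 in serious disease: control risk 0.30 × 0.10 = 3%, treated risk 3% × 0.65 = 1.95%. A two-proportion test with pooled variance and no continuity correction gives 78.7%, against 80% stated.

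So the planning figures reproduce, with serious disease taken to be hospitalization only.

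**Coding of a COVID-19 death outside hospital**

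- 9.2.2.6: an event, because the diagnosis resulted in death.
- 9.6.4 (b), literally: not an event, because no hospitalization was required.
- 9.6.4 censoring rule: not censored, because the death is due to COVID-19.
- Result in (b): outcome 0, still in the denominator.

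**Cases lost.** The documents give no count of such deaths. Let m be that count (assumed), added to the planned 200. Share of cases missed = m / (200 + m):

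- m = 5: 5/205 = 2.4%
- m = 10: 10/210 = 4.8%
- m = 20: 20/220 = 9.1%
- m = 40: 40/240 = 16.7%

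These people would be at most 40/6450 = 0.62% of the non-cases (6650 − 200), so the non-case group is hardly altered. Out-of-hospital Grade 4 cases would add to m.

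**Effect on a risk ratio.** Let f be the proportion of serious cases never hospitalized. With no false positives,

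estimated RR = true RR × (1 − f_exposed) / (1 − f_unexposed).

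For a true RR of 2, with all values of f assumed:

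- Equal f: 2 × (1 − f)/(1 − f) = 2.00
- 10% exposed, 5% unexposed: 2 × 0.90/0.95 = 1.89
- 20% exposed, 5% unexposed: 2 × 0.80/0.95 = 1.68
- 30% exposed, 10% unexposed: 2 × 0.70/0.90 = 1.56
- 5% exposed, 20% unexposed: 2 × 0.95/0.80 = 2.38

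Under-capture alone does not bias the RR. Unequal under-capture does, and its sign depends on which group is admitted less readily.

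**The case against.** **The censoring sentence may show the opposite intent.** Exempting COVID-19 deaths from censoring could mean they are to be counted as events. That is a fair reading, but then the wording of (b) contradicts the intent and still needs correcting. The main SAP may settle it; the two protocol sections should agree in any case.

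**Hospitalization is a recurring and defensible choice.** Sections 2.1.8, 9.4.4 and 9.5.1 all refer to it, and an observational model may use a narrower outcome than the randomized comparison. Objective 1.2.2.9 names infection and COVID-19-related cardiovascular outcomes, not out-of-hospital severity. This limits the importance of the point. It does not explain why death is left out.

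**The model already adjusts.** Section 9.6.4 stratifies by global burden of disease region and controls for hypertension, diabetes, kidney disease and obesity. That reduces distortion from differing access to hospital. It leaves differences within region, and it does not recover a death coded as a non-event.

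**Stronger readings that the documents do not support.** A reader might infer that someone who dies before the next annual sample also counts as uninfected under (a). No section says so. Table 9.4.4-1 "Assumes sample size of 6650 with evaluable COVID-19 antibody results equally distributed between pitavastatin and placebo groups", which points to non-evaluable, and an earlier sample could already be positive. A reader might also infer that estimates are necessarily pulled toward 1. That needs exposed participants to be hospitalized less often; if older or sicker people are admitted more readily, the bias reverses. No section supports a direction or a value.

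**Conclusion.** The mismatch between 9.2.2.6 and outcome (b) of 9.6.4 is real. On a literal reading, COVID-19 deaths and Grade 4 cases outside hospital become non-cases. The size is unknown because the documents give no out-of-hospital share. On the assumed range of 5 to 40 such deaths the loss is modest, and the RR is biased only if the missed share differs by host factor, in a direction that cannot be stated in advance.

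The point is confined to secondary, observational host-factor models. It rests on the protocol text alone, since the main REPRIEVE SAP was not available. It is worth correcting because the correction is small and uses an endpoint that the trial has already defined.

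**What to change.** - **Outcome (b):** define it by the serious COVID-19 endpoint of 9.2.2.6, so that COVID-19 deaths and Grade 4 cases count as events. Report hospitalization alone as a sensitivity analysis.
- **Outcome (a):** keep it serological. State that a participant with no sample after the infection is non-evaluable, not negative.
- **Deaths:** state in 9.6.4 that a COVID-19 death is an event in (b), and check that the main REPRIEVE SAP agrees.

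Adding recorded diagnoses to (a) is not advised. Section 9.4.4 favours antibody testing because it does not depend on local testing rates, and diagnosed COVID-19 already has its own endpoint in 9.2.2.6.

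Cost: a change of analysis wording. Section 9.2.2.6 already requires these events to be identified, and all deaths are adjudicated for cause (6.4.2). The downside is that a small number of non-hospitalized cases will rest on adjudicated cause of death or site grading. Some may be hard to assign: the death categories in 9.2.2.2 name no COVID-19 category, and 9.2.1 allows for deaths of undetermined cause. The sensitivity analysis shows how much depends on them.

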**More detailed analysis plans are provided in the REPRIEVE Statistical Analysis Plan.**

## **10.0 PHARMACOLOGY PLAN**

Not applicable.

## 11.0 DATA COLLECTION AND MONITORING AND ADVERSE EVENT REPORTING

### 11.1 Records to Be Kept

Electronic case report forms (CRF) are available on the DMC website. Participants must not be identified by name on any CRFs. Participants will be identified by the patient identification number (PID), screening number (SN), and study identification number (SID) provided by the DMC upon randomization.

### 11.2 Role of Data Management

Instructions concerning the recording of study data on eCRFs will be provided by the DMC. Each CRS is responsible for recording the data in a timely fashion.

It is the responsibility of the DMC to ensure the quality of computerized data for each study. This role extends from protocol development to generation of the final study databases.

### 11.3 Clinical Site Monitoring and Record Availability

**Monitoring visits may be conducted on-site or remotely. Remote visits may include remote source document verification using methods specified for this purpose by NIAID. Remote monitoring visits may be performed in place of, or in addition to, onsite visits to ensure the safety of study participants and data integrity [FDA, 2021]. The site will make available study documents for site monitors to review utilizing a secure platform that is HIPAA and 21 CFR Part 11 compliant. Potential platform options include: Veeva SiteVault, site-controlled SharePoint or cloud-based portal, direct access to Electronic Medical Record (EMR), and Medidata Rave Imaging Solutions. Other secure platforms that are 21 CFR Part 11 compliant may be utilized, as allowed by the DAIDS Office of Clinical Site Oversight (OCSO).**

### 11.4 Expedited Adverse Event Reporting to DAIDS

#### 11.4.1 Adverse Event Reporting to DAIDS

Requirements, definitions, and methods for expedited reporting of AEs are outlined in Version 2.0 of the DAIDS EAE Manual, which is available on the RSC website at <https://rsc.niaid.nih.gov/clinical-research-sites/manual-expedited-reporting-adverse-events-dais>.

The DAIDS Adverse Experience Reporting System (DAERS), an Internet-based reporting system, must be used for expedited AE reporting to DAIDS. In the event of system outages or technical difficulties, expedited AEs may be submitted via the DAIDS EAE Form. For questions about DAERS, please contact DAIDS-ES (now part of the NIAID Clinical Research Management System) at

[[contact]](mailto:[contact]). Site queries may also be sent from within the DAERS application itself.

Sites where DAERS has not been implemented will submit expedited AEs by documenting the information on the current DAIDS EAE Form. This form is available on the RSC website: <https://rsc.niaid.nih.gov/clinical-research-sites/paper-eae-reporting>. For questions about EAE reporting, please contact the RSC ([[contact]](mailto:[contact])).

#### 11.4.2 Reporting Requirements for this Study

The SAE Reporting Category, as defined in Version 2.0 of the DAIDS EAE Manual, will be used for this study with certain exceptions as noted below. Unless the site investigator considers the following events to be study drug-related, **DO NOT REPORT** them as EAEs:

- AIDS-defining events (see MOPS for a listing)
- REPRIEVE MACE (see [section 9.2.1](#) for complete listing) and related CVD events: CVD death, MI, stroke, TIA, unstable angina, peripheral ischemia, coronary or peripheral reperfusion procedures, heart failure, **and all deaths** (because they are components of the primary endpoint or additional adjudicated CVD endpoint). See MOPS for details about reporting CVD Endpoints).
- **COVID-19 hospitalizations.**

**NOTE: COVID-19 is a novel disease that has emerged since protocol version 5.0 was distributed. Given our evolving understanding of this viral infection, and the likelihood of subclinical cardiac injury during COVID-19 hospitalization, the requirement for reporting COVID-19 infection has been outlined in greater detail in the MOPS.**

The study agents for which expedited reporting are required are pitavastatin and placebo for pitavastatin.

#### 11.4.3 Grading Severity of Events

The Division of AIDS Table for Grading the Severity of Adult and Pediatric Adverse Events (DAIDS AE Grading Table), corrected Version 2.1, July 2017, is available on the DAIDS RSC website at <https://rsc.niaid.nih.gov/clinical-research-sites/daids-adverse-event-grading-tables>.

#### 11.4.4 Expedited AE Reporting Period

The expedited AE reporting period for this study is the entire study duration for an individual participant (from study enrollment until study completion or discontinuation of the participant from study participation for any reason).

After the protocol-defined AE reporting period, unless otherwise noted, only SUSARs (suspected unexpected serious adverse reactions) as defined in Version 2.0 of the EAE Manual, will be reported to DAIDS if the study staff become aware of the events on a passive basis (from publicly available information).

## 12.0 PARTICIPANTS

### 12.1 Institutional Review Board (IRB) Review and Informed Consent

This protocol and the informed consent document ([Appendix I](#)) and any subsequent modifications will be reviewed and approved by the IRB/EC responsible for oversight of the study. A signed consent form will be obtained from the participant (or legal representative). The consent form will describe the purpose of the study, the procedures to be followed, and the risks and benefits of participation. A copy of the consent form will be given to the participant or legal representative, and this fact will be documented in the participant's record. Risks, including potential risks of pitavastatin, and protection against risk are described in the accompanying sample informed consent form.

### 12.2 Participant Confidentiality

All laboratory specimens, evaluation forms, reports, and other records that leave the site will be identified by coded number only to maintain participant confidentiality. All records will be kept locked. All computer entry and networking programs will be done with coded numbers only. Clinical information will not be released without written permission of the participant, except as necessary for monitoring by the ACTG, IRB/EC, FDA, NHLBI, NIAID, OHRP, and other local, US, and international regulatory entities as part of their duties, or the industry supporters or designee.

### 12.3 Study Discontinuation

The study may be discontinued at any time by the ACTG, IRB/EC, FDA, NIAID, NHLBI, OHRP, or the industry supporter, or other government agencies as part of their duties to ensure that research participants are protected.

### 12.4 Women and Minorities

REPRIEVE (A5332) will aim to recruit women and minority participants commensurate with the population demographic for HIV in the US. The prevalence of HIV among women in the US is approximately 22%, while over half of **PWH** in the US are minorities (CDC 2014).

## 13.0 PUBLICATION OF RESEARCH FINDINGS

Publication of the results of this trial will be governed by NHLBI and NIAID policies.

#### 14.0 BIOHAZARD CONTAINMENT

All dangerous goods and materials, including diagnostic specimens and infectious substances, must be transported using packaging mandated by CFR 42 Part 72. Please refer to instructions detailed in the International Air Transport Association (IATA) Dangerous Goods Regulations.

#### 15.0 STUDY GOVERNANCE

- There is an Executive Committee, a DSMB, and an External Advisory Board.
- There are various other operational committees to ensure that the trial progresses smoothly.
- There is a Clinical Events Committee (CEC) charter.

## SITES PARTICIPATING IN THE MECHANISTIC SUBSTUDY of REPRIEVE (A5333s)

The Mechanistic Substudy of REPRIEVE (A5333s) is open to selected sites that are participating in the REPRIEVE (A5332) study.

## EXECUTIVE SUMMARY

Title	Effects of Pitavastatin on Coronary Artery Disease and Inflammatory Biomarkers: Mechanistic Substudy of REPRIEVE (A5333s)
Indication	Assess the effects of statins on critical plaque and inflammatory characteristics to understand mechanism of action in HIV
Location	Selected sites of the REPRIEVE (A5332) study
Brief Rationale	The Mechanistic Substudy of REPRIEVE (A5333s) will determine, among HIV-infected persons, potential statin effects to halt progression of non-calcified atherosclerotic plaque and to stabilize morphologic features of plaque vulnerability. Moreover, the study will identify biological factors mediating these changes – be it lipid parameters, such as LDL cholesterol, or markers of inflammation and immune activation.
Study Design and Duration	Randomized, placebo-controlled multicenter substudy of REPRIEVE (A5332) in 800 subjects, with individual subjects participating in the substudy for 2 years.
Treatment	Pitavastatin 4 mg PO daily or placebo for pitavastatin.
Primary Objective	To determine the effects of pitavastatin on the morphology and composition of non-calcified coronary atherosclerotic plaque (NCP), including the progression of plaque volume and whether these effects are modulated by markers of inflammation and immune activation.
Key Secondary Objectives	
 
1. The effects of pitavastatin on the progression of high risk plaque features including low attenuation plaque and positive remodeling.
 
2. The effects of pitavastatin on detailed markers of immune activation, immune activation, inflammation, coagulation, and traditional CVD risk indices including detailed parameters of glucose homeostasis (insulin, glucose and related indices of insulin resistance such as HOMA-IR, HgbA1c).
 
3. The relative contributions of baseline and pitavastatin induced changes in HIV-specific immune activation and traditional risk factors, including LDL, on the presence and progression of coronary plaque and high risk morphological features in HIV.
 

Primary Endpoint	Noncalcified plaque volume on coronary computed tomography angiography (CCTA)
Secondary Endpoints	High risk plaque features on CCTA Detailed immune phenotyping measures and inflammatory and coagulation indices as well as detailed measures of glucose homeostasis
Abbreviated Study Flow	Subjects will be coenrolled at specific sites participating in the Mechanistic Substudy of REPRIEVE (A5333s). Enrollment and treatment will be identical as in REPRIEVE (A5332), but endpoints will be collected over 2-year study duration for each enrolled patient.

